
ASSESSMENT SCHEDULE
	
Clinical examinations (including height at baseline only, weight, ECOG PS, and vital signs), laboratory tests (including complete blood counts, serum chemistry and coagulation), 12-lead ECG, concomitant medications, and AEs (NCI CTCAE v.4.03) will be obtained prior to drug administration, every cycle before treatment administration and up to 30 days after the last study treatment administration. Laboratory tests (including complete blood counts, and serum chemistry) will be also obtained at D8 and D15 for the first 2 cycles and complete blood counts only at D8 for the subsequent cycles, before treatment administration where applicable.
 
An ECG will be obtained within 7 days prior to first drug administration and at the end of treatment.
 
Efficacy evaluation:
 
Tumor assessments (CT-scan or MRI and any other exams as clinically indicated) will be performed at baseline and every 6 weeks during the study treatment period from baseline to disease progression even if the patient discontinued study treatment before progressive disease or study cut-off whichever comes first. Confirmatory radiological evaluation will be performed at least 4 weeks after initial documentation of response.

	
PK evaluation/immunogenicity: Assessments will be performed using blood-samples collected at baseline, at specific time points of each cycle, and at the end of treatment and follow-up visits as specified in the PK/immunogenicity flow chart (Section 1.4).
 
Biomarker analyses: CA6 expression will be assessed by IHC at a central laboratory on the most recent available tumor sample (ie, archive tumor tissue at diagnosis, archive tumor tissue at surgery, or most recent metastatic biopsy). Blood samples for circulating CA6 and [REDACTED] will be collected as specified in the flow chart (Section 1.2). [REDACTED] (Section 1.2). [REDACTED] (Section 1.2). After study treatment discontinuation, patients will be followed every 6 weeks until death, study cut-off date or withdrawal of patient's consent.

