1.3 FOOTNOTES FOR STUDY FLOW CHART

- a **Prescreening:** the preselection test on CA6 positivity will be determined by centralized IHC on FFPE slides collected from the most recent available tumor samples (6 FFPE slides). Extra slides, if available, will be preserved and used to support the development of a potential in vitro diagnostic assay for a registration trial. The CA6 IHC staining will be performed at a centralized laboratory; a prescreening Informed Consent will be signed by the patient for this purpose. The positivity of CA6 is defined by IHC with membrane staining of $\geq 30\%$ (2+, 3+) of tumor cells for Part 1 and Part 2a, and membrane staining of at least 1% positive tumor cells at intensity $\geq 1+$ and $< 30\%$ of tumor cells at intensity 2+, 3+ for Part 2b. Both CA6 cytosolic and membrane percent staining at intensity 1+, 2+, and 3+ will be recorded.
- b **Screening** assessments must be performed prior to first IMP administration: patients must have confirmed CA6 expression as assessed centrally. Baseline evaluation should be completed within 1 week prior to initiation of therapy, except for tumor assessment and ocular tests that may be performed within 3 weeks prior to the first IMP administration. Results of these tests should be reviewed by the Investigator prior to randomization. If any laboratory tests are abnormal, these must be repeated within 2 days before the first IMP administration.
- c Only for Part 1: all eligible patients will be randomly assigned to one of the 2 dose level treatment cohorts using an IVRSIWRS. Study treatment should be started within 3 calendar days from randomization.
- d D1 and D8: Cycle 1 D1D8 refers to the days the patient receives the initial dose of IMP. D1 of Cycle 2 and of each subsequent cycle corresponds to D22 of the previous cycle. Before Cycle 1, evaluations such as ECOG PS, body weight, signs and symptoms, physical examination, hematology, and blood chemistry should be performed less than 7 days before IMP administration and should be repeated within 2 days before IMP administration if abnormal. For further cycles, assessment can be done on the day of infusion (before infusion) or the day before.

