- e **Physical examination** will include: examination of major body systems, height (at baseline only), body weight, ECOG PS, and vital signs (temperature, blood pressure). At the follow-up visit, only ECOG PS and weight will be collected. Signs and symptoms will be reported in the eCRF as AEs only if they are still present at the time of first IMP administration.
- f **Hematology:** hemoglobin, WBC with differential, platelet counts. These tests will be done weekly for Cycles 1 and 2. If Grade 4 neutropenia occurs, assess ANC every 2-3 days until ANC $\geq 0.5 \times 10^9/L$.
- g **Coagulation:** INR.
- h **Blood chemistry:** liver function tests: AST, ALT, total bilirubin, conjugated bilirubin, AP, electrolytes: sodium, potassium, calcium, phosphate, and chloride. Renal function tests: creatinine and BUN or urea. Others: glucose, LDH, albumin, and total proteins. These tests will be done weekly during the 2 first cycles then every 3 weeks for subsequent cycles, except for BUN and chloride that will be done weekly only during the first cycle. Additional tests will be performed when clinically appropriate. In case of Grade ≥ 3 liver function abnormal tests, additional tests will be done every 2 to 3 days until recovery to baseline value.
- i **Serum pregnancy test:** women of child-bearing potential must have a negative serum pregnancy test result within 7 days prior to the initial dose of IMP and at the end of treatment evaluation (between D22 and D30 after the last IMP administration). The serum pregnancy test will also be performed before each cycle, only in countries where it is a regulatory requirement.
- j **12-lead ECG** is required at baseline and at end of treatment. To be repeated as clinically indicated.

- k* **SAR566658 administration:** on Day 1 and Day 8 of each treatment cycle, the patient's BSA will be determined using the current weight and baseline height. For patients with a BSA >2.0 m², the dose will be calculated on the basis of 2.0 m² BSA. Premedication with histamine H1 antagonist is required: diphenhydramine 50 mg given orally approximately 1 hour before SAR566658 administration.

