8.2.3.2 Treatment delay

At Day 22, a treatment delay ≥ 4 days should be justified (ie, to be reported in the eCRF). Study treatment may be delayed up to 2 weeks to allow recovery from acute toxicity. In case of a delay due to IMP-related AEs ≥ 2 weeks (except for alopecia), the patient will be withdrawn from the treatment.

The dose of SAR566658 will be modified in case of AEs. Dose modifications are summarized in [Table 3](#).

Table 3 - Dose modifications for SAR566658

Adverse event	Grade 2	Grade 3	Grade 4
Diarrhea	Delay ^a next infusion until recovery (Grade ≤1). No dose reduction required.	On Day 8, omit the dose. On Day 22, delay ^a next infusion until recovery (Grade ≤1): - 1st episode: reduce dose by 1 dose level, - 2nd episode: reduce dose by 1 more dose level, - 3rd episode: withdraw from study treatment.	
Creatinine increase	No delay, in case of creatinine >1.5 x ULN to calculate creatinine clearance (CLCr) ^b on D21: - If ≥50 mL/min, no dose modification, - If clearance ≥30 mL/min and < 50 mL/min, reduce dose by 1 dose level, - If clearance <30 mL/min, withdraw from study treatment.		
Peripheral neuropathy	No delay. Reduce by 1 dose level.	Delay ^a next infusion until recovery (Grade ≤1): - 1st episode: reduce dose by 1 dose level, - 2nd episode: reduce dose by 1 more dose level, - 3rd episode: withdraw from study treatment.	Withdraw from study treatment.
Total bilirubin elevation	In case of bilirubin >1.5 x ULN: On Day 8, omit the dose. On Day 22, delay ^a until recovery to bilirubin ≤1.5 x ULN and then reduce by 1 dose level. If no recovery after 2 dose reductions, withdraw from study treatment.		
Transaminases elevation	On Day 8, omit the dose. On Day 22, delay ^a until recovery to AST/ALT Grade ≤1. No dose adjustment.	On Day 8, omit the dose. On Day 22, delay ^a until recovery to AST/ALT Grade ≤1: - 1st episode: reduce dose by 1 dose level, - 2nd episode: reduce dose by 1 more dose level, - 3rd episode: withdraw from study treatment.	Withdraw from study treatment.

Dose reduction levels provided in [Table 2](#).

^a A maximum of 2 weeks delay at D22, otherwise the patient will be withdrawn from study treatment.

^b As per Cockcroft-Gault formula; see [Appendix E](#).

Abbreviations: ALT: Alanine aminotransferase; AST: Aspartate aminotransferase; D: day; ULN: upper limit of normal.

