10.1.4 During study treatment

At Cycle 1 Day 1, the inclusion/exclusion criteria and informed consent must be rechecked before any study-specific procedure is performed. All procedures should be performed prior to study treatment administration unless specified otherwise.

The following procedures will be performed:

- **Physical examination** (Cycles 1 and 2: Days 8, 15, and 21; subsequent cycles: Days 8 and 21) including major body systems examination, body weight, ECOG PS, and vital signs (temperature and blood pressure).
- **Concomitant medications** (to be assessed continuously throughout the on-treatment period and to be recorded at every cycle).
- **Adverse events** (to be assessed continuously throughout the on-treatment period and to be recorded at every cycle).
- **Tonometry** (without dilatation) to measure intraocular pressure at the end of Cycle 6 only.
- **Hematology** will be done before each study treatment administration (-3 day window is allowed) and in case of fever or infection: WBC with differential count, hemoglobin, platelet count.

In addition, hematology will be performed every week (Day 8 and Day 15) during the first 2 cycles (± 1 day window is allowed), then during subsequent cycles at Day 8 and in case of fever or infection.

- **Blood Chemistry** will be done before each study treatment administration (-3 days window is allowed): sodium, potassium, calcium, phosphate, chloride, creatinine, creatinine clearance if creatinine $>1.5 \times$ ULN, BUN or urea, AST, ALT, total bilirubin, conjugated bilirubin, alkaline phosphatase, glucose, LDH, albumin, and total protein. In addition, blood chemistry (sodium, potassium, calcium, phosphate, chloride, creatinine, creatinine clearance if creatinine $>1.5 \times$ ULN, BUN or urea, AST, ALT, total bilirubin, conjugated bilirubin, alkaline phosphatase, glucose, LDH, albumin, and total protein) will be performed every week (Day 8 and Day 15) during the 2 first cycles (± 1 day window is

allowed), except for BUN and chloride that will be done weekly only during the first cycle.

- **Coagulation tests** (Day 21 of each cycle): INR.
- **Serum pregnancy test** (Day 1 of each cycle from Cycle 2 onwards): for women of child-bearing potential, only in countries where it is a regulatory requirement.
- **Blood sample for circulating CA6** (Cycle 1 Day 1 only): 1 sample will be taken prior to study treatment administration.
- [REDACTED]
- [REDACTED]
- [REDACTED]

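### From Cycle 3, Table 3's Day 8 liver omission rule has no clearly scheduled liver test to act on

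*Protocol*

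**What the plan says.** **Dosing.** Footnote k to the study flow chart (Protocol 1.3) places administration "on Day 1 and Day 8 of each treatment cycle".

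**Dosing rule.** Protocol 8.2.3.2, Table 3, bilirubin row: "In case of bilirubin >1.5 x ULN: On Day 8, omit the dose". The transaminase row gives the same Day 8 instruction for Grades 2 and 3. Neither row is limited to certain cycles. On Day 22 both rows delay the next infusion; for bilirubin the delay lasts "until recovery to bilirubin ≤1.5 x ULN and then reduce by 1 dose level". The creatinine row works differently: "No delay, in case of creatinine >1.5 x ULN to calculate creatinine clearance", with the clearance calculated on D21.

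**Testing schedule from Cycle 3.**
- Synopsis, Assessment schedule: "complete blood counts only at D8 for the subsequent cycles".
- Footnote h, on blood chemistry, which includes the liver tests: "These tests will be done weekly during the 2 first cycles then every 3 weeks for subsequent cycles".
- SAP 2.1.4.4: hematology on Day 8 and Day 21, clinical chemistry on Day 21.
- Protocol 10.1.4: chemistry "will be done before each study treatment administration (-3 days window is allowed"), followed by an added requirement for Day 8 and Day 15 in the first two cycles.

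**Timing windows.** Footnote d: "For further cycles, assessment can be done on the day of infusion (before infusion) or the day before". Section 10.1.4 allows 3 days before the infusion.

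**The concern.** A rule that withholds a dose on a laboratory value needs that value before the dose. From Cycle 3 the Day 8 test that the synopsis keeps is the blood count, which has no row in Table 3. It drops chemistry, which supplies the two laboratory values on which Table 3 orders Day 8 omission.

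The pre-cycle test does not fill the gap. An elevation known before Day 1 already holds that infusion under the Day 22 rule, so only a later value can newly trigger a Day 8 omission.

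The protocol expects about 30 sites. A site that takes 10.1.4 literally will have a liver result before Day 8. A site that follows the synopsis or footnote h will not. The same patient could be dosed at one and omitted at the other.

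**Working it through.** The plan states no figure on this point. The check compares the texts and then counts days.

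**1. Two readings of 10.1.4**

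*Literal.* Each administration includes Day 8, because footnote k names both days and SAP section 2 treats administration and infusion as the same thing. Day 8 chemistry is then required in every cycle, which contradicts the synopsis, footnote h and SAP 2.1.4.4.

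*Once per cycle.* The chemistry bullet adds Day 8 for Cycles 1-2, and the hematology bullet adds Day 8 for later cycles. Both additions would be redundant for Day 8 if the base rule already covered it. The synopsis has the same structure: a per-cycle base rule, then extra days. The column alignment of the flow chart grid is not reliable in the text reviewed, but the number of marks fits this reading. Before the end-of-treatment mark, the later cycles carry one chemistry mark against two for hematology. All four places then agree, and no Day 8 liver value is scheduled from Cycle 3.

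**2. Infusions affected (once-per-cycle schedule)**

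Over c cycles there are 2c infusions. Cycles 1-2 have Day 8 chemistry, so c - 2 infusions have no scheduled liver value after the pre-cycle test.
- c = 4: (4 - 2)/8 = 2/8 = 25%
- c = 8 (24 weeks, four 6-weekly scans): (8 - 2)/16 = 6/16 = 37.5%
- Literal 10.1.4: 0/8 and 0/16

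The choices of 4 and 8 cycles are illustrative; the documents give no expected treatment duration.

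**3. Age of the last test at the Day 8 infusion**

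Age = 7 + d, where d is the number of days the test precedes Day 1.
- d = 0: 7 days
- d = 1 (Day 21 of the previous cycle): 8 days
- d = 3 (the 10.1.4 window): 10 days

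Under literal 10.1.4 the test is 0 to 3 days old.

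**4. Time to the next scheduled test**

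With no cycle delay the next Day 1 is Day 22. Time from Day 8 = 22 - d2 - 8, where d2 is the same lead time for the next test. This is 14 days (d2 = 0) to 11 days (d2 = 3).

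**5. Gap between consecutive scheduled tests**

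Gap = 21 + d1 - d2, with d1 and d2 each 0 to 3, so 18 to 24 days. Scheduled testing misses a rise entirely only if it starts and ends inside one such gap.

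**6. What existing safeguards cover**
- Footnote h allows extra tests when clinically appropriate. An asymptomatic rise gives no prompt.
- Footnote h requires retesting every 2 to 3 days after a Grade 3 or higher liver abnormality. That starts only once the abnormality is known, whereas Table 3 acts from Grade 2.
- A rise lasting to the next pre-cycle test triggers the Day 22 delay. Protocol 10.4.2 then makes it a reportable AE because dosing changed.
- Under SAP 2.4.5.4 and 2.5.6, any value measured on treatment, scheduled or not, counts toward the worst laboratory grade.

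**The case against.** The strongest case against is that the plan is coherent and the reduced testing deliberate. On the once-per-cycle reading nothing conflicts. Table 3 says what to do with an abnormal value and does not itself order a test. Patients have had two cycles of weekly chemistry. What remains is a new, silent rise within 7 to 10 days of an acceptable result.

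Phase I gives little cause for alarm. Protocol 4.1.2, describing 89 patients, notes low-grade liver abnormalities. The two dose-limiting toxicities among 8 patients at 240 mg/m² q3w, the same dose intensity as 120 mg/m² D1D8, were diarrhea and keratitis.

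Most of this stands, and it is why the point is minor. It does not remove the gap: if the reduction was deliberate, the Day 8 liver rule from Cycle 3 depends on an unscheduled result and 10.1.4 needs clearer wording. Phase I had 17 patients on 90 mg/m² D1D8 and none on 120 mg/m² D1D8.

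Stronger inferences that a reader might draw are not supported:
- *The protocol plainly contradicts itself.* That is one of two fair readings, and the less favored one.
- *The SAP gives sites a competing order.* An analysis plan does not direct blood draws; it shows only how its authors understood the schedule.
- *The ±1 day window at Day 8 in Cycles 1-2 permits sampling after the infusion.* Section 10.1.4 opens by requiring procedures before administration unless otherwise specified, and the synopsis also asks for pre-dose sampling.

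**Conclusion.** The point holds on either reading of 10.1.4, as a minor one. Read literally, 10.1.4 disagrees with the synopsis, footnote h and the SAP. Read as once per cycle, the documents agree, but Table 3's Day 8 liver rule has no scheduled value from Cycle 3. That leaves 25% of infusions over 4 cycles, or 37.5% over 8, relying on a test 7 to 10 days old. These are counts of infusions, not of harm; the documents give no rate of transient liver rises.

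The conclusion assumes that Table 3 applies in every cycle, which is inferred from the absence of a limit, and that cycles are not delayed. A reader might infer that liver toxicity would go undetected or that the results would be biased. The documents do not support either. Persisting rises are caught at Day 22, measured values enter the laboratory tables, and both doses follow the same schedule. ORR, alpha, power and the Cycle 1-2 safety endpoint are unaffected.

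**What to change.** **Schedule.** In the synopsis, the flow chart with footnote h, and section 10.1.4, state that from Cycle 3 AST, ALT and total bilirubin are drawn before the Day 8 infusion, at the blood draw already made for counts, and reviewed before dosing. State also that the full panel is done once per cycle before Day 1. Leave weekly testing in Cycles 1-2 as it is, and update SAP 2.1.4.4 for consistency. Say openly that this narrows the literal wording of 10.1.4 for the other analytes. Of those, only creatinine has a Table 3 rule, and it is tied to D21. If the sponsor meant 10.1.4 literally, correct the synopsis, footnote h and the SAP instead.

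**Windows.** Leave the 7-day Cycle 1 baseline window unchanged. For later infusions choose either footnote d's window (day of infusion or day before) or the 3 days in 10.1.4, and use it in both places. Choosing 3 days loosens footnote d and should be stated as such.

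**Alternative.** Stating that Table 3's Day 8 liver action applies only when a result is available would cost no assay. It would settle the wording but leave silent rises untested.

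**Cost.** Wording, plus one AST/ALT/bilirubin set per cycle from Cycle 3 compared with the once-per-cycle schedule: 2 per patient over 4 cycles, 6 over 8. The upper bound, if all 63 patients stayed on treatment, is 63 x 2 = 126 or 63 x 6 = 378 sets. No extra visit or needle stick is needed. Day 8 omissions and recorded worst grades may rise slightly. Compared with literal 10.1.4 there is no extra liver assay.

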1 FLOW CHARTS

[figure not shown]
1.1 GRAPHICAL STUDY DESIGN

1.1.1 Overall study design

Abbreviations: D: day; q3w: every 3 weeks; SD: selected dose; TNBC: triple negative breast cancer.

1.1.2 Schematic study schedule (Part 1 and Part 2)

Abbreviations: +ve: positive; D: day; ICF: informed consent form; IVRS/IWRS: Interactive Voice/Web Response System; q3w: every 3 weeks; W: week.

1.2 STUDY FLOW CHART

Day	Prescreening ^a	Screening (prior to first infusion) ^b		R A N D O M I Z A T I O N ^c	Treatment Cycle 1					Treatment Cycle 2				Subsequent cycles			End of treatment (Day 30 after last infusion)	Follow-up period ^l
		-21 to 1	-7 to 1		-1	1 ^d	8 ^d	15	21	1 ^d	8 ^d	15	21	1 ^d	8 ^d	21		
CA6 expression status (archival tumor tissue) – central IHC/ prescreening Informed consent	X																	
Inclusion/exclusion criteria/ Informed Consent		X																
Demography and medical/disease history		X																
Physical examination ^{e/} signs and symptoms			X				X	X	X		X	X	X		X	X	X	X
Hematology ^f			X				X	X	X		X	X	X		X	X	X	
Coagulation ^g			X					X			X				X		X	
Blood chemistry ^h			X				X	X	X		X	X	X		X		X	
Serum pregnancy test ⁱ			X						X				X				X	
12-lead ECG ^j			X														X	
SAR56658 administration ^k						X	X			X	X			X	X			
Primary prophylaxis for ocular event ^l						X	X			X	X			X	X			
Hospitalization ^m					X	X												
AE assessment ⁿ		Continuously throughout the study period																
Concomitant medication ^o		Continuously throughout the study period																
PK/immunogenicity assessment ^p		See PK/immunogenicity flow chart																
Specific ocular tests ^q		X																
Tumor assessment ^r		X											X				X	X

Day	Prescreening ^a	Screening (prior to first infusion) ^b		Treatment Cycle 1					Treatment Cycle 2				Subsequent cycles			End of treatment (Day 30 after last infusion)	Follow-up period ^t
		-21 to 1	-7 to 1	-1	1 ^d	8 ^d	15	21	1 ^d	8 ^d	15	21	1 ^d	8 ^d	21		
Circulating CA6 ^s					X												
██████████					X				X				X			X	X
██████ ██████					X											X	
██████████ ██████					X												
Further anticancer therapy																	X
Survival status ^u																	X

1.3 FOOTNOTES FOR STUDY FLOW CHART

- a **Prescreening:** the preselection test on CA6 positivity will be determined by centralized IHC on FFPE slides collected from the most recent available tumor samples (6 FFPE slides). Extra slides, if available, will be preserved and used to support the development of a potential in vitro diagnostic assay for a registration trial. The CA6 IHC staining will be performed at a centralized laboratory; a prescreening Informed Consent will be signed by the patient for this purpose. The positivity of CA6 is defined by IHC with membrane staining of $\geq 30\%$ (2+, 3+) of tumor cells for Part 1 and Part 2a, and membrane staining of at least 1% positive tumor cells at intensity $\geq 1+$ and $< 30\%$ of tumor cells at intensity 2+, 3+ for Part 2b. Both CA6 cytosolic and membrane percent staining at intensity 1+, 2+, and 3+ will be recorded.
- b **Screening** assessments must be performed prior to first IMP administration: patients must have confirmed CA6 expression as assessed centrally. Baseline evaluation should be completed within 1 week prior to initiation of therapy, except for tumor assessment and ocular tests that may be performed within 3 weeks prior to the first IMP administration. Results of these tests should be reviewed by the Investigator prior to randomization. If any laboratory tests are abnormal, these must be repeated within 2 days before the first IMP administration.
- c Only for Part 1: all eligible patients will be randomly assigned to one of the 2 dose level treatment cohorts using an IVRSIWRS. Study treatment should be started within 3 calendar days from randomization.
- d D1 and D8: Cycle 1 D1D8 refers to the days the patient receives the initial dose of IMP. D1 of Cycle 2 and of each subsequent cycle corresponds to D22 of the previous cycle. Before Cycle 1, evaluations such as ECOG PS, body weight, signs and symptoms, physical examination, hematology, and blood chemistry should be performed less than 7 days before IMP administration and should be repeated within 2 days before IMP administration if abnormal. For further cycles, assessment can be done on the day of infusion (before infusion) or the day before.
- e **Physical examination** will include: examination of major body systems, height (at baseline only), body weight, ECOG PS, and vital signs (temperature, blood pressure). At the follow-up visit, only ECOG PS and weight will be collected. Signs and symptoms will be reported in the eCRF as AEs only if they are still present at the time of first IMP administration.
- f **Hematology:** hemoglobin, WBC with differential, platelet counts. These tests will be done weekly for Cycles 1 and 2. If Grade 4 neutropenia occurs, assess ANC every 2-3 days until ANC $\geq 0.5 \times 10^9/L$.
- g **Coagulation:** INR.
- h **Blood chemistry:** liver function tests: AST, ALT, total bilirubin, conjugated bilirubin, AP, electrolytes: sodium, potassium, calcium, phosphate, and chloride. Renal function tests: creatinine and BUN or urea. Others: glucose, LDH, albumin, and total proteins. These tests will be done weekly during the 2 first cycles then every 3 weeks for subsequent cycles, except for BUN and chloride that will be done weekly only during the first cycle. Additional tests will be performed when clinically appropriate. In case of Grade ≥ 3 liver function abnormal tests, additional tests will be done every 2 to 3 days until recovery to baseline value.
- i **Serum pregnancy test:** women of child-bearing potential must have a negative serum pregnancy test result within 7 days prior to the initial dose of IMP and at the end of treatment evaluation (between D22 and D30 after the last IMP administration). The serum pregnancy test will also be performed before each cycle, only in countries where it is a regulatory requirement.
- j **12-lead ECG** is required at baseline and at end of treatment. To be repeated as clinically indicated.

- k* **SAR566658 administration:** on Day 1 and Day 8 of each treatment cycle, the patient's BSA will be determined using the current weight and baseline height. For patients with a BSA >2.0 m², the dose will be calculated on the basis of 2.0 m² BSA. Premedication with histamine H1 antagonist is required: diphenhydramine 50 mg given orally approximately 1 hour before SAR566658 administration.
- l* **Primary prophylaxis for eye disorders** is required in each eye (vasoconstrictor and steroid eye drops, cold mask) at the time of infusion and for 2 additional days after infusion for steroid eye drops only (making a total of 3 days of ophthalmic topical steroid including Day 1 of each cycle). Topical artificial tears are recommended to be instilled in each eye up to 6 times per day during the whole study treatment period.
- m* **Hospitalization** for the first IMP administration is recommended for safety monitoring, until at least 6 hours after the end of IMP administration. Ambulatory hospitalization can be considered at the Investigator's discretion.
- n* **Adverse event/serious adverse event assessment:** the period of safety observation extends from the date the study informed consent is signed, until at least D30 after the last IMP administration. Concomitant medication will be recorded in the eCRF. Adverse events will be recorded according to NCI CTCAE version 4.03 ([Appendix D](#)).
- o* **Concomitant medication** will be recorded in the eCRF from 21 days prior to the first study treatment administration, before every cycle during the study treatment period, and for up to 30 days after the final dose of study drug. Once the patient has withdrawn from study treatment, concomitant medication should only be recorded if used to treat new or unresolved study treatment-related adverse events.
- p* **PK/immunogenicity:** see detailed flow chart ([Section 1.4](#)).
- q* **Specific complete ocular examination** at baseline will include: assessment of ocular/visual symptoms, visual acuity, full ocular tests including slit lamp with fluorescein under dilatation, and Schirmer's test preferably with anesthetics. In patients with any ocular/visual symptom(s) (eg, blurred vision, photophobia) the complete ocular tests will be repeated at the time of the occurrence of the ocular toxicity. Then, visual acuity, slit lamp examination under dilatation, and Schirmer's test will be repeated once weekly until resolution to Grade 1. In case of recurrent ocular toxicity observed in subsequent cycles, visual acuity and slit lamp examination with fluorescein under dilatation, and Schirmer's test preferably with anesthetics will be performed at the time of the event onset, then weekly until resolution to Grade 1. Moreover, tonometry will be performed at screening, at the end of Cycle 6 (with a time window of 4 days preceding the following cycle administration), whenever clinically indicated, and at End of Treatment, to assess and monitor intraocular pressure. At screening, tonometry will be performed with and without dilation, and only without dilation at the subsequent time points.
- r* **Tumor assessment** as per RECIST1.1: CT-scan or MRI and any other examinations as clinically indicated will be performed to assess disease status at baseline, every 6 weeks during the study treatment period until radiological disease progression or study cut-off, whichever comes first, and at the end of study treatment, except if already done at last cycle. Confirmatory radiological evaluation will be performed at least 4 weeks after initial documentation of response.
- s* [REDACTED]
- t* **Follow-up period (every 6 weeks):** during the follow-up period, SAEs (regardless of relationship with study treatment) and IMP-related AEs ongoing at the end of study treatment, and any new IMP-related AE/SAE will be followed until resolution or stabilization (stabilization is defined as an event ongoing without any change for at least 3 months). Patients achieving stable disease, complete or partial response should be followed until radiological disease progression, death, study cut-off, or withdrawal of patient's consent, whichever comes first. For patients who discontinue study treatment prior to radiological documentation of disease progression, a tumor assessment will be performed every 6 weeks. Date of disease progression and further anticancer treatment will be collected at the follow-up visit.
- u* **Survival status:** During the follow-up period, patients without documented disease progression but not on treatment at the second cut-off date will be followed every 6 weeks to collect survival status for a further 6 months or until documented disease progression, death, or withdrawal of consent, whichever comes first.

Abbreviations: AE: adverse event; ALT: alanine aminotransferase; ANC: absolute neutrophil count; AP: alkaline phosphatase; AST: aspartate aminotransferase; BSA: Body Surface Area; BUN: Blood Urea Nitrogen; [REDACTED]; CT: Computed Tomography; D: Day; ECOG: Eastern Cooperative Oncology Group; eCRF: electronic Case Report Form; FFPE: formalin-fixed paraffin-embedded; IHC: immunohistochemistry; IMP: investigational medicinal product; INR: International Normalized Ratio; IVRS/IWRS: Interactive Voice/Web Response System; LDH: lactate dehydrogenase; MRI: Magnetic Resonance Imaging; NCI CTCAE: National Cancer Institute Common Terminology Criteria for Adverse Events; PS: performance status; RECIST: Response Evaluation Criteria in Solid Tumors; SAE: serious adverse event; TNBC: triple negative breast cancer; WBC: white blood cell.

